4.1. Overview

Subjects will be screened for eligibility as detailed above. Study participants will be consented prior to the administration of any procedure. Following the screening assessment and confirmation that all criteria for entry into the study are met, eligible subjects will be assigned to 2 different groups based on their baseline venous CRP level: CRP \geq 1 and CRP<1. Participants within each group will then be randomized in a 1:1 fashion to one of the two treatment arms: a) CRP-consistent antidepressant selection or b) CRP-inconsistent antidepressant selection.

Table 1.

Visit Week	Week 0*		Week 2 ⁺	Week 4 ⁺	Week 6 ⁺	Week 8	Week 12 ⁺
	Screening	Baseline					
Visit Day Window	0		14 (+/-3)	28 (+/-3)	42 (+/-3)	56 (+/-3)	84 (+/-3)
Informed Consent and Eligibility Screening							
Informed Consent	X						
Eligibility Screening	X						
The Demographics Form	X						
Clinical, General Health, and Medical History Surveys							
The Self-Administered Comorbidity Questionnaire (SCQ)	X						
Prior and Concomitant Medication and Treatment and Adverse Events	X	X	X	X	X	X	X
Antidepressant Treatment Response Questionnaire (ATRQ)	X						
Fagerstrom Test of Nicotine Dependence	X						
Depression Severity Measurement Tools							
M.I.N.I. (7.0) Structured Diagnostic Interview	X						
Hamilton Depression Rating Scale	X					X	X
Inventory of Depressive Symptomatology (IDS)		X	X	X	X	X	X
Concise Health Risk Tracking Scale (CHRT)		X	X	X	X	X	X
Work and Social Adjustment Scale (WSAS)		X	X	X	X	X	X
The Temporal Experience of Pleasure Scale (TEPS)		X	X	X	X	X	X
Behavioral Inhibition System/ Behavioral Approach System (BIS/BAS) Scale		X	X	X	X	X	X

(TABLE 1 continued on next page)

Anxiety Symptoms							
Generalized Anxiety Disorder 7-item (GAD-7)		X	X	X	X	X	X
State Trait Anxiety Inventory (STAI)		X	X	X	X	X	X
Side Effects and Adherence							
Patient Adherence to Antidepressant Medication Questionnaire (PAQ)			X	X	X	X	X
Frequency, Intensity, and Burden of Side Effects			X	X	X	X	X
Cognition and Behavioral							
Flanker Test		X				X	
Digit Symbol Substitution Test		X				X	
Behavioral Phenotyping - 24 Hours Substance Use		X				X	
Physical Examination and Collection of Biospecimens							
Physical Examination	X						
Vital Signs (BP, HR, RR, Temperature, Pain)	X	X*	X**	X**	X**	X**	
HT/WT/BMI, Waist/ Hip Circumference	X	X*	X**	X**	X**	X	
Blood Collection: CBC, BMP, TSH, Lipid Panel, Hemoglobin A1c, CRP		X					X++
Urine Toxicology Screen	X						
Urine Pregnancy Test	X						
Blood Based Immunomarkers							
Optional Venous Blood Draw for Biobanking		X				X	
Optional Finger Prick		X					
Electroencephalogram (EEG)							
Optional EEG: Resting State		X				X	

*Screening and baseline will take place on the same visit. If not possible, baseline will be completed within 2 weeks after screening. Vital signs, BMI, and Waist:Hip ratio will be updated.

** Obtained during in office visits only.

+ Weeks 2, 4, 6, and 12 visits may be performed remotely when necessary.

++ CRP and HbA1C only

4.2. Screening and Baseline Visit

Screening

Duration: 2 hours

The screening phase will start with the informed consent procedures. Once patients agree to participate in the study by signing the informed consent document, a medical and psychiatric history will be taken and a physical examination will be performed, as outlined in Table 1. The purpose is to ensure that only appropriate patients are entered into the study. The investigator will determine that the patients meet eligibility criteria and will collect the demographic and medical data permitting full characterization of the patients. Patients found to be in potential need of hospitalization due to their degree of suicidal ideation at screening will be referred to the nearest emergency room.

If the participant meets all of the inclusion criteria and none of the exclusion criteria, he/she will proceed to the baseline portion of the visit.

*Baseline – Week 0*Duration: 1 hour 15min **OR** up to 2 hours

1. Self-Report Questionnaires (30 min)
2. Clinician/Assessor Rated Assessments (HAM-D, M.I.N.I and ATRQ) (45min)
3. Neurocognitive and behavioral phenotyping tasks (30 minutes).
 - o Including optional EEG (30 minutes)
4. Blood Draw (15 minutes)

4.3. Randomization

Patients will be assigned to one of two groups based on their baseline CRP level as measured by a venous blood sample: CRP \geq 1 or CRP<1. Participants from both groups will then be randomized in a 1:1 fashion to one of the two treatment arms: CRP consistent antidepressant selection or CRP inconsistent antidepressant selection.

- **CRP-consistent antidepressant selection**

If venous blood CRP<1, then prescribe escitalopram.
If venous blood CRP \geq 1, then prescribe bupropion XL

- **CRP-inconsistent antidepressant selection**

If venous blood CRP \geq 1, then prescribe escitalopram
If venous blood CRP<1, then prescribe bupropion XL

4.4. Study Visits*Week 2, 4, and 6*

Duration: 1 hour

1. Self-Report Questionnaires (30 min)
2. Prior and Concomitant Medication and Treatment, Adverse Events (5-10 min)
3. Clinician General Interview (15min)
4. Assessment of vital signs and weight (10 minutes).

*Week 8 (Exit Phase)*Duration: 2 hours **OR** up to 2 hours and 35 minutes

1. Self-Report Questionnaires (30 min)
2. Prior and Concomitant Medication and Treatment (5-10 min)
2. Clinician General Interview and Hamilton Depression Rating Scale (25 min)
4. Assessment of vital signs and weight (15 min)
5. Neurocognitive and behavioral phenotyping tasks (30 minutes).
 - o Including optional EEG (30 minutes)
6. Blood draw (15 min)

Post Study Follow Up

Week 12

Duration: 1 hour

Consists of a phone call and self-administered questionnaires. The phone call will last approximately 20 minutes and will include a clinician rated Hamilton Depression Rating Scale. A series of self-report questionnaires will be sent electronically and will take approximately 40 minutes.

4.4.1. Participant Compensation

Essential to the study is appropriate support for participants' time and effort contributing to the study. Participants will receive monetary remuneration for participation in the study to compensate for time burden and travel arrangements and will be paid for each eligible visit using UT Southwestern ClinCard, per IRB regulations. Compensation for study procedures will be made each time a complete study is performed throughout the study duration. Bus passes or other help with transportation and/or parking expenses may also be available, if needed.

Participants completing a screening and baseline visit inclusive of data collection and biospecimens will be compensated (\$25). Participants will be paid (\$10) for completed visits at week 2, 4, 6, and 8.

Participants who complete the follow up visit via telephone at week 12 will be compensated for completed assessments (\$10) and self-report questionnaires (\$10).

4.4.2. Costs

Participants or insurance providers will not be charged for events related to this study (i.e., screening procedures, laboratory procedures). Study medications (i.e. escitalopram or bupropion-XL) will also be provided at no cost. UT Southwestern Medical Center will not pay for doctor visits, other treatments, or tests that are NOT part of this study. Compensation for an injury resulting from the participation in this research is not available from the University of Texas Southwestern Medical Center at Dallas. If a situation arises in which a participant is unable to collect their prescription at the designated study pharmacy, they will be reimbursed for the cost of their medication pick-up, using the receipt of the transaction as proof of purchase.

4.5. Laboratory/Diagnostic Procedures

Blood samples will be collected from participants by trained phlebotomists, who will draw the sample using standard venipuncture procedures, through a single venipuncture using a small gauge needle. Universal precautions will be observed by the phlebotomists during all draws. Each tube will be labeled and packaged for processing and storage.

Screening Phase - Week 0

Once the patient has signed the informed consent document, the urine drug screen and pregnancy test will be performed (if applicable)

Baseline Phase - Week 0

About 30 ml (~2 tablespoons) of venous blood will be collected and the following tests will be completed: Complete Blood Count, Basic Metabolic Panel, Lipid Panel, Hemoglobin A1c, TSH levels, and CRP levels. Later analysis of other immunomarkers (eg. IL-1, IL-6, TNF alpha), metabolism (eg. lipids, glucose

tolerance, amino acids, kyni), neurological function (eg. brain-derived neurotrophic factor, monoamine receptors, etc) and genetic testing will also be performed. The rest of the blood samples will be stored indefinitely until the sample runs out or it is destroyed.

Week 8 - Exit Phase

About 25 ml (~2 tablespoons) of venous blood will be collected and used for CRP and later analysis of other immunomarkers level measurements (eg. IL-1, IL-6, TNF), metabolism (eg. lipids, glucose tolerance, amino acids, etc), neurological function (eg. brain-derived neurotrophic factor, monoamine receptors, etc) and genetic testing will also be performed. The rest of the blood samples will be stored indefinitely until the sample runs out or it is destroyed.

4.6 Optional Finger Prick

Participants will have the option to participate in a sub-study that will compare venous blood CRP levels with capillary blood CRP levels. The purpose of this sub-study is to examine if the latter is accurate and can be used in future studies and clinical practice. During the baseline visit, 2-5 drops of capillary blood will be collected using a finger prick. The CRP levels on the capillary blood will be analyzed and compared to those obtained using venous blood obtained via venipuncture.

4.7 Optional Electroencephalogram (EEG)

Participants will have the option to participate in a sub-study that will acquire 10 minutes of resting state EEG at baseline and Week 8 to provide measures of functional network connectivity. The purpose of this sub-study is to determine the predictive utility of EEG-derived measures in treatment response to escitalopram and bupropion.

4.7.1 Electroencephalogram (EEG) Procedures

Participants will undergo EEG recordings at baseline and at Week 8. EEG is performed by placing an elastic cap containing electrodes on the participant's scalp. These electrodes are previously soaked in a potassium chloride saline solution (similar to salt water) in order to better conduct electrical signals at the scalp. The technician ensures correct alignment of the cap and the quality of measured signals. This process takes approximately 10-15 minutes. The participant's brain activity is then recorded for 5 minutes as they sit quietly with their eyes open, generally fixating a marked point in front of them. This procedure is repeated for 5 minutes but with the participant's eyes closed as the rest quietly but awake. The cap is then removed and the participant can pat dry their hair with a provided towel. The total time estimate for completion of the EEG collection at each visit is approximately 30 minutes. The EEG workgroup will ensure that adequate training, standardization of measures, and validation of equipment is maintained for data consistencies and quality control purposes.

5. Treatment

5.1. Overview

The current study will use two FDA-approved medication for MDD: escitalopram and bupropion-XL. Systematic reviews and meta-analyses have failed to find significant differences in treatment outcomes in head-to-head comparisons of SSRIs and bupropion. In this context, the treatment provided in this clinical trial is expected to have similar risks to standard clinical care.

Escitalopram is a widely-used SSRI, which is FDA-approved for MDD in people aged 12 or older.⁴⁰ The efficacy is similar to other SSRIs but escitalopram is known for fewer side-effects and fewer pharmacological interactions making it well-tolerated and commonly used in clinical practice.⁴¹ The medication is commercially available in the generic form or under the brand name Lexapro. The generic medication will be provided in this study. The compound will be obtained from a commercial pharmacy. Since this is study is open-label, the medication will be dispensed to the participants in its usual commercial form. We will provide escitalopram in tablets of 5 mg, 10 mg, 15 mg and 20 mg.

Bupropion is a commonly used norepinephrine-dopamine reuptake inhibitor that is FDA-approved for MDD.⁴¹ Its antidepressant effects are comparable to SSRIs and other antidepressants.⁴²⁻⁴⁴ Bupropion has good overall tolerability.⁴⁵ Bupropion is commercially available in the generic form as well as under the brand names Wellbutrin, Zyban and Aplenzin. The medication comes in three formulations: regular bupropion, bupropion sustained-release (SR) and bupropion extended-release (XL). Bupropion-XL will be provided in this study (tablets of 150 mg and 300 mg). This formulation has the advantage of being used just once a day, while the other formulations need to be taken twice or three times a day. In addition to a better dosing schedule, bupropion-XL has theoretically fewer side-effects.⁴⁴

5.2. Mechanisms of action

Escitalopram exerts its antidepressant actions through blockage of the serotonin reuptake pump leading to synaptic changes that result on increased serotonergic transmission.⁴¹ It is a “clean” SSRI - i.e. no significant secondary pharmacological actions and no known immunological effect.²³ Escitalopram usually starts working in 2 to 4 weeks.

Bupropion XL is a commonly used norepinephrine-dopamine reuptake inhibitor. As a result, this medication is believed to increase norepinephrine and dopamine neurotransmission. Evidence from in vitro and pre-clinical studies suggest that bupropion has an additional anti-inflammatory action.⁴⁶⁻⁴⁸ Therefore, this antidepressant would be particularly useful for MDD with underlying systemic inflammation. Bupropion antidepressant effects usually start in 2 to 4 weeks after its initiation.

5.3. Dosing Schedule

Escitalopram will be started at 5 mg/day during the first week of treatment. The dose will then be increased to 10mg/day, and can be increased to 20 mg/day if side-effects allow and QIDS-C is higher than 5. Dose can be decreased to 5 mg by clinician discretion such as to increase tolerability or better manage side-effects. 5 mg will be the lowest dose allowed in the study.

Bupropion-XL will be started at 150 mg/day and increased to 300 mg/day after one week. This dose can be increased to 450 mg/day (divided in 2 doses) at Week 2 or later if side-effects allow and QIDS-C is higher than 5. Clinicians may opt to titrate bupropion-XL in a slower fashion in cases that might increase tolerability or better manage side-effects. 150 mg will be the lowest dose allowed in the study.

After study completion at week 8, participants who wish to remain on treatment will be given a four-week supply of study drug while they transition care.

The medications schedule described above is based on previous trials.^{49,50}

5.4. Concomitant Therapy

All concomitant medications taken during the study will be recorded in the Concomitant Medication Log for each patient, along with dosage information and start and stop dates. Allowed concomitant medications include any prescription or over-the-counter medication not specifically excluded by the protocol. Patients requiring excluded drugs will be discontinued from the study.

6. Sources of Research material

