3.2. Methods

70 eligible subjects will be assigned to one of two groups based on their baseline venous CRP level: CRP < 1 or CRP ≥ 1 . Participants in both groups will then be randomly assigned in a 1:1 fashion to one of two treatment arms: a) CRP consistent antidepressant selection or b) CRP inconsistent antidepressant selection. All subjects will be followed for 56 (+/- 3) days (8 weeks) to examine the efficacy of the study treatments. The treatment phase is followed by a remote follow-up call and electronic self-report questionnaires at 12 weeks.

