3.4. Subject Eligibility

Inclusion Criteria

A subject will be eligible for inclusion only if all of the following criteria are met:

- Women and men ages 18-65
- Diagnosis of Major Depressive Disorder according to Diagnostic and Statistical Manual of Mental Disorders, Fifth Edition (DSM-5) criteria confirmed by the Mini International Neuropsychiatric Interview (MINI).
- Have a score of 14 or higher on the Hamilton Scale for Depressive Symptomatology as assessed by trained clinicians.

Exclusion Criteria

A potential participant will NOT be eligible for participation in this study if any of the following criteria are met:

- Any antidepressant use within the last 8 weeks
- Active infection or uncontrolled autoimmune disease
- Currently on oral corticosteroids or active immune suppressive therapy (methotrexate, cyclosporine, anti-cytokines medications, etc. Note that nonsteroidal anti-inflammatory drugs - NSAIDs - will be allowed).
- Current diagnosis of uncontrolled HIV, hepatitis C or significant immunodeficiency
- Subject has a history of moderate or severe substance or alcohol use disorder according to DSM-5 criteria, except nicotine or caffeine, within 3 months before signing informed consent form.
- Positive urine drug test for illicit substances or substances used out of the context of prescription
- Cognitively unable to give informed consent
- Pregnant or breastfeeding women, women of childbearing potential who are not using an accepted means of birth control, or women with a positive urine pregnancy test
- History of seizure disorder
- Previous significant adverse reaction to escitalopram or bupropion
- History of non-response to adequate doses of escitalopram or bupropion XL
- Current use of concomitant psychotropic agents (anticonvulsants, benzodiazepines, hypnotics, opiates, triiodothyronine (T3), modafinil, psychostimulants, buspirone, melatonin, folate, L-methylfolate, s-adenosyl methionine, lithium) not on the same dose for at least four weeks prior to study entry or who do not agree to continue at the same dose during the acute phase of the study.
- Lifetime history of bipolar disorder, schizophrenia, schizoaffective disorder or other psychotic disorder except for Major Depressive Disorder with psychotic features in prior episode.
- Current anorexia nervosa or bulimia nervosa per Mini International Neuropsychiatric Interview (MINI).

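### Section 5.4 with 3.4 does not clearly bar a patient from newly starting a non-antidepressant psychotropic between randomisation and Week 8

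*Protocol*

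**What the plan says.** Section 5.4 (Concomitant Therapy) has all concomitant drugs logged with dose and start and stop dates. It then gives the rule: "Allowed concomitant medications include any prescription or over-the-counter medication not specifically excluded by the protocol". Its last sentence takes patients who need an excluded drug out of the study. The section has no list of drugs prohibited on treatment.

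The only drug exclusions are in section 3.4, introduced by "A potential participant will NOT be eligible for participation in this study if any of the following criteria are met". Three items matter here:

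- Antidepressants: "Any antidepressant use within the last 8 weeks".
- Oral corticosteroids and active immune suppressive therapy, if the patient is on them at entry.
- Psychotropics: "Current use of concomitant psychotropic agents (anticonvulsants, benzodiazepines, hypnotics, opiates, triiodothyronine (T3), modafinil, psychostimulants, buspirone, melatonin, folate, L-methylfolate, s-adenosyl methionine, lithium", and the list closes there. The exclusion applies to users who are "not on the same dose for at least four weeks prior to study entry". It also applies to users unwilling to hold that dose through the acute phase.

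Section 3.1 describes an open-label trial. Section 3.2 sets the eight-week follow-up "to examine the efficacy of the study treatments". Section 6.1 makes the primary endpoint self-reported remission, a QIDS-SR score of 5 or less.

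**The concern.** The permission in 5.4 is only as tight as the exclusions it points to, and for psychotropics those were written for people already taking a drug at entry. If a patient who was not taking one starts a hypnotic, an anxiolytic or an augmenting agent in week 3, the protocol gives no clear answer. On one reading the drug is allowed, the patient continues, and a remission at Week 8 is counted under the assigned strategy although another drug may have produced it. On the other reading the patient is removed from the study and the Week 8 outcome may be lost.

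The setting makes this more than a matter of style. Staff and patients know the treatment, and the endpoint is a self-reported cutoff. Section 6.4 says that the parent scale, the IDS-SR, covers insomnia and anxiety, which such drugs target; the protocol does not say which 16 items form the QIDS-SR. The stable-dose condition in 3.4 shows that the protocol wants background psychotropics held constant. The wording secures this only for existing users.

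**Working it through.** The protocol has no figure of its own to reproduce on this point. The check is a reading of the two sections together, followed by an illustration of scale.

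**Which new starts are covered by 5.4 read with 3.4?**

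| Drug started after randomisation | Text in 3.4 | Most natural reading on treatment |
|---|---|---|
| Second antidepressant | Barred outright in the eight weeks before entry | Excluded drug; patient leaves under 5.4 |
| Oral corticosteroid or immune suppressant | Barred outright if current at entry | Excluded drug; patient leaves under 5.4 |
| Dose change of a listed psychotropic already taken at entry | Agreement to hold the dose in the acute phase | Covered, if the acute phase means the eight treatment weeks |
| New start of a listed non-antidepressant psychotropic | Admitted at a stable dose; nothing on non-users | Not clearly barred |
| New start of an antipsychotic | Not named; coverage by the general term is open | Not clearly barred |

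The last two rows are the gap. Carrying the 3.4 list into treatment does not close it, because 3.4 does not exclude the 13 listed psychotropics outright; it admits them when stable. If all of them counted as excluded drugs under 5.4, a validly enrolled patient on a stable benzodiazepine would have to leave the study. If they do not count as excluded, a new start is allowed. The promise to keep the same dose does not settle the matter, since a non-user has no dose to keep.

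**Scale of one event.** Inputs: 70 patients (section 3.2: "70 eligible subjects will be assigned to one of two groups based on their baseline venous CRP level"), randomised 1:1 within CRP stratum. The remission rate p is not in the protocol; 30–50% in both arms is an assumption.

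- Per arm: 70 / 2 = 35.
- Shift in the arm difference per changed remission status: 1/35 = 2.86 points.
- Standard error of the difference: sqrt(2 × p × (1 − p) / 35).

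| p (assumed) | Standard error (points) | 2.86 / standard error |
|---|---|---|
| 0.30 | sqrt(0.42/35) = 10.95 | 0.26 |
| 0.40 | sqrt(0.48/35) = 11.71 | 0.24 |
| 0.50 | sqrt(0.50/35) = 11.95 | 0.24 |

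The number of new starts is not given, and none is assumed. With no starts, or with equal starts of equal effect in both arms, the expected shift is about zero. Each strategy arm contains both study drugs, so co-medication prompted by one drug's side effects may partly balance.

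**The case against.** The strongest reply is the last sentence of 5.4. It governs patients already in the study, and it has content only if the 3.4 exclusions carry into treatment. This stands for drugs that 3.4 bars outright. A reader might infer that 5.4 permits augmentation with any mood-active drug, including a second antidepressant. The documents do not support that, because it would leave the removal sentence with almost nothing to act on. Nor are the psychotropic limits purely entry conditions, since existing users must hold their dose during the acute phase.

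It can also be said that a newly started psychotropic is by definition not on a stable dose and so falls within the intent of 3.4. That is a sensible clinical reading, but the text does not state it, and 5.4 asks for a specific exclusion.

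Naming antipsychotics may look like a drafting preference, because the general term could cover them and most psychotic disorders are excluded. That is fair as to likely frequency, but the coverage remains open.

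Concomitant drugs are logged and reviewed at every visit, so new starts can be identified, and their handling in the analysis may be in the SAP, which was not available. That is accepted, but an SAP cannot tell clinicians what they may prescribe.

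Finally, a blanket bar on everything in the 3.4 list would catch melatonin, folate and short opiate courses. That objection is right and shapes the remedy.

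**Conclusion.** The point holds as a narrow ambiguity. New starts of non-antidepressant psychotropics, antipsychotics included, are not clearly barred between randomisation and Week 8. The protocol also leaves open whether such a patient continues or is removed.

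The effect is probably small. One changed outcome is worth 2.9 points, or 0.24–0.26 of a standard error, on the assumption of 30–50% remission in both arms. This prices a single hypothetical patient and does not estimate bias. A reader might infer that the gap favours one strategy, but nothing in the protocol gives a direction or a frequency. This is a cheap improvement and does not threaten the trial's validity.

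**What to change.** 1. In 5.4, state that the 3.4 drug exclusions apply through Week 8. Add that, apart from study-drug titration under 5.3, none of the following may be newly started or dose-changed for mood, anxiety or sleep in that period: a non-study antidepressant, antipsychotic, lithium, T3, psychostimulant, modafinil, buspirone, anticonvulsant, benzodiazepine or hypnotic. Supplements and short courses for medical reasons are logged and do not trigger stopping.
2. Replace the removal sentence in 5.4. A patient who needs an excluded drug receives it and stops study drug if clinically indicated. The Week 8 QIDS-SR is still collected, and the patient stays in the randomised comparison. Sensitivity analyses for such cases are left to the SAP.

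Item 1 makes added treatment less frequent. Item 2 protects the primary outcome when it happens anyway. A remission on an added drug would still count in its randomised arm, so separating its effect remains a matter for sensitivity analysis.

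The cost is a rewritten paragraph in 5.4 and perhaps a few more study-drug discontinuations. No new data are needed, since the log already holds doses and dates and the Week 8 questionnaire is already scheduled.

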3.1. Overview

The current study is single site, randomized, open label 8-week clinical trial comparing the efficacy of CRP-consistent antidepressant selection vs CRP-inconsistent antidepressant selection. Venous levels of CRP will be measured by an FDA cleared Point of Care Smart analyzer (Diazyme Laboratories) and/or Quest Diagnostics, which provides the CRP concentration within few minutes. The study will use a stratified randomization (i.e. separate randomization schemes for patients with POC CRP ≥ 1 and POC CRP < 1). This will assure that the four study groups have similar sample sizes: 1) escitalopram with CRP < 1 , 2) bupropion-XL with CRP < 1 , 3) escitalopram with CRP ≥ 1 , 4) bupropion-XL with CRP ≥ 1 . We anticipate that participants with higher inflammation (CRP ≥ 1) will have higher remission rates with bupropion-XL than escitalopram, while individuals with low levels of systemic inflammation (CRP < 1) will remit more frequently with escitalopram when compared to those treated with bupropion XL. A sub-study will compare POC CRP levels based on the blood source: venous blood obtained by venipuncture vs capillary blood obtained via fingerstick.

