6.1. Outcome Measures

The primary study endpoint will be remission rates based on the 16-item Quick Inventory of Depressive Symptomatology, Self-Report (QIDS-SR), which will be extracted from the 30-item Inventory of Depressive Symptomatology (IDS-SR). QIDS-SR measures MDD severity; a score of 5 or less is considered remission. The secondary study endpoints will be: a) improvement in social and occupational function according to the 5-item self-administered Work and Social Adjustment Scale and b) side effect measures using the 3-item Frequency, Intensity, and Burden of Side Effects Rating (FIBSER) scale.

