9.1. Safety Measures

Minimal risk is expected from the medications as FDA approved low doses will be administered initially, side-effects to these doses monitored and dosage adjustments made according to guidelines. If physical adverse effects are intolerable at the lowest therapeutic dose, subjects may leave the study and will be offered an alternative treatment in consultation with their provider. Minimal risk is also expected from venipuncture and finger stick for POC CRP testing. These will be further minimized by having laboratory work performed only by trained and certified staff, following aseptic procedures, and ascertaining that patient does not have an active infection or taking immunosuppressive treatment (as part of eligibility criteria).

All research personnel are trained in safety precautions in the event the patient needs immediate clinical management or an imminent clinical issue is identified.

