9.3. Reasons for Early Termination

Acceptable reasons for early termination from the randomized clinical trial include the following: 1) request of patient, 2) decision of physician, 3) serious adverse event and 4) protocol violation. Patients will be assessed for suicidal ideation at every visit. Subjects who, in the opinion of the assessing clinician have a worsening of suicidal ideation that renders them at increased risk for study participation will be removed from the study and given an appropriate clinical referral.

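### Early exit is written as exit from the study, and nothing keeps the Week 8 QIDS-SR or WSAS for those who leave

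*Protocol*

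**What the plan says.** Section 3.2 makes a general promise: "All subjects will be followed for 56 (+/- 3) days (8 weeks) to examine the efficacy of the study treatments". Section 6.1 sets the endpoint: "The primary study endpoint will be remission rates based on the 16-item Quick Inventory of Depressive Symptomatology, Self-Report (QIDS-SR"), with a score of 5 or less counted as remission. The WSAS is a secondary endpoint. Section 6.1 names no time point. I take Week 8, because section 3.1 calls this a "single site, randomized, open label 8-week clinical trial" and Week 8 ends treatment.

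The exit rules are worded differently:

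- Section 5.4, on concomitant drugs: "Patients requiring excluded drugs will be discontinued from the study".
- Section 9.3, on its general list: "Acceptable reasons for early termination from the randomized clinical trial include the following". Four reasons follow: patient request, physician decision, serious adverse event and protocol violation.
- Section 9.3, on suicidality: subjects judged to have a "worsening of suicidal ideation that renders them at increased risk for study participation will be removed from the study".
- Section 9.1, on intolerable effects at the lowest therapeutic dose: "subjects may leave the study and will be offered an alternative treatment in consultation with their provider".

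Section 9.4 lets the adverse-event reporting period end before Week 12 for those who discontinue prematurely. The only collection it ties explicitly to the time after the last dose is for serious adverse events and pregnancy, both for 30 days. Table 1 schedules the IDS and WSAS at baseline and Weeks 2, 4, 6, 8 and 12. It has no early-termination column, and its footnote allows remote visits at Weeks 2, 4, 6 and 12 but not at Week 8.

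**The concern.** Stopping a drug and stopping measurement are different events, and the protocol treats them as one. A site that follows sections 5.4, 9.1 and 9.3 literally has no instruction to ask for a Week 8 QIDS-SR or WSAS after exit. A site that follows section 3.2 literally would ask. Which happens is left to local reading.

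The missing values would not all be accidental. Removal for worsening suicidal ideation is closely tied to the course of the depression, and a physician's decision may be. A comparison of randomised arms on remission is protected by randomisation only as far as outcomes are obtained for those randomised. With 70 participants and a binary primary endpoint, a few losses matter. They are also hard to justify, because the primary endpoint is a self-report scale that needs neither study drug nor a clinic visit.

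This is not a detail that can wait for the SAP. An SAP decides how to handle collected and missing values, but it cannot use questionnaires that were never sent.

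**Working it through.** **Text.** There is no stated figure to reproduce: the protocol gives a sample size but no dropout, remission or power figures. I read sections 3.2, 4.1, 4.4, 5.3, 5.4, 6.1 and 9.1 to 9.4 and Table 1 for any rule on outcome assessment after exit.

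1. Every exit rule names the study or the trial as what is left. None refers to study drug alone.
2. Section 9.4 shows that discontinuing shortens at least one stream of data collection.
3. Section 3.2 covers all subjects but does not mention those who have exited, and no passage says which statement prevails.
4. The Week 8 visit in section 4.4 is labelled an exit phase, but it is the scheduled end of treatment, not an assessment triggered by early exit.

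**Scale.** Inputs are 70 participants (sections 3.2 and 3.3) and 1:1 allocation (sections 3.2 and 4.3), so about 35 per arm.

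- One outcome: 1/35 = 2.9 percentage points of an arm's remission rate.
- Suppose k outcomes are lost in each arm, with r1 and r2 observed remitters. Full-data remission lies between r/35 and (r + k)/35 in each arm. The difference lies between (r1 − r2 − k)/35 and (r1 − r2 + k)/35, a range 2k/35 wide.
- For assumed k: k = 1 gives 2/35 = 5.7 points, k = 4 gives 8/35 = 22.9 points, and k = 7 gives 14/35 = 40.0 points.

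These widths assume nothing about who exits. They are outer limits, not estimates of bias.

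**Whether an analysis rule can repair it.** Let p be true remission in an arm, e the exit rate, and s the share of those exiting who would have remitted. Among those remaining, the observed rate is (p − s·e)/(1 − e). If exits count as non-remitters, it is p − s·e. All rates below are invented.

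- *Equal true remission.* p = 0.40 and e = 0.15 in both arms, s = 0.40 against 0.20. Those remaining: (0.40 − 0.06)/0.85 = 0.400 against (0.40 − 0.03)/0.85 = 0.435, a spurious 3.5 points. Exits as non-remitters: 0.340 against 0.370, a spurious 3.0 points. The sign reverses if the two shares swap.
- *Different true remission.* p = 0.50 against 0.30, with e = 0.15 and s = 0.30 in both arms. Those remaining: (0.50 − 0.045)/0.85 = 0.535 against (0.30 − 0.045)/0.85 = 0.300, or 23.5 points where the truth is 20.0. Exits as non-remitters: 0.455 − 0.255 = 20.0 points.

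So equal exit rates and equal shares do not in general make the analysis of those remaining unbiased. What each rule does depends on quantities that the protocol does not give and that could not be learned without outcomes after exit.

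**The case against.** The strongest reply is that section 3.2 already covers everyone, or that section 9.3 simply lists exceptions to it. Either reading is possible. They lead to opposite conduct, which is the reason to reconcile the text.

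A second reply is that the target of estimation belongs to the SAP. If exit itself is defined as failure, no value after exit is needed for remission. That stands as a choice the SAP may make. But without the data that choice is forced, no sensitivity analysis could use actual Week 8 values, and the WSAS has no equally natural failure value.

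Third, the link between section 5.4 and outcome is weaker than it looks. Section 5.4 has no drug list. A reader might infer that starting or changing a benzodiazepine or hypnotic forces exit, but this rests on carrying over an entry criterion in section 3.4 that permits such drugs at a stable dose. Other drugs excluded there, such as oral corticosteroids, have no evident tie to depression outcome. Section 9.3 is the firmer ground.

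Fourth, some losses would remain. A participant who withdraws consent cannot be followed, so the ranges above overstate what can be recovered. Scales at Weeks 2, 4 and 6 give partial information for people who exit late.

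Finally, a reader might infer that open-label treatment tilts exits toward one arm. The documents do not support that. Each arm contains both drugs, so drug-specific exits may partly balance overall, though not necessarily within a CRP stratum. Knowing the drug reveals the arm only to someone who also knows the CRP stratum.

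**Conclusion.** The point holds as a gap and an internal conflict in the conduct rules, and the sponsor should correct it. The protocol words exit as exit from the study, promises 56 days of follow-up for all, and keeps neither the QIDS-SR nor the WSAS at Week 8 for those who leave.

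The size is conditional: 2.9 points of an arm's remission rate per lost outcome, and a range of 22.9 points for the difference if four are lost per arm, which is an assumed number. The conclusion assumes Week 8 as the primary time point, about 35 per arm, and exit rules followed literally.

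It would go too far to say that the trial will be biased, or in which direction. No exit rate or pattern is given, and only losses not due to withdrawn consent can be recovered.

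**What to change.** Reconcile sections 3.2, 5.4, 9.1, 9.3 and 9.4 by distinguishing stopping study drug from ending outcome follow-up. All treatment, removal and safety decisions stay under the protocol's existing rules.

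- State that randomised participants who stop early and have not withdrawn consent to follow-up are asked for the IDS-SR (from which the QIDS-SR is taken) and the WSAS at Week 8. Say expressly how this fits with the removal rule in section 9.3.
- Amend the Table 1 footnote so that these self-reports may be collected remotely at Week 8. The route exists: for Week 12, section 4.4 says "A series of self-report questionnaires will be sent electronically and will take approximately 40 minutes".
- Record the date of and reason for each exit, and whether the Week 8 scales were obtained.

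The cost is an amendment and one short questionnaire set per person who exits. At the $10 that section 4.4.1 pays for a completed visit, and assuming 10% to 20% of 70 exit (7 to 14 people), that is about $70 to $140. Staff would also carry out the evaluation already required by section 9.2 if a response shows risk of self-harm.
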